5.4.4 Supportive analyses

A sensitivity analysis will be performed on primary efficacy endpoint after imputing the week 24 missing values by last observed carried forward (LOCF) technique, for patients having baseline and at least one post baseline value.

5.5 SECONDARY OBJECTIVES

Population for the analysis

All secondary efficacy analyses will be based on the full analysis set (FAS). For all safety analyses, the safety analysis set will be used.

5.5.1 Efficacy variables and analysis

The secondary efficacy endpoints are described in section 1.2.1.

The mean and percent change in tumor volume from baseline to Week 4, 12 and 24 will be presented along with the 90% confidence interval (CI). If data is found to be skewed, CIs for median will also be generated. Incidence rates for patients with \geq 20% reduction in tumor volume and its exact CI will be reported at Week 4 and 12.

Summary statistics will be provided for each disease related symptoms (headaches, visual disturbance, fatigue, symptoms specific to man and woman) at each visits. Change from baseline scores will be also summarized at each visit for all symptoms.

Time to response, defined as time from the first injection to first evaluation where patient achieve tumor volume reduction of at least \geq 20%, will be listed for all patients. If a patient has not achieved tumor response, the time of last assessment will be indicated as censoring time.

Kaplan-Meier analysis will be performed for time to response aiming to compute the median time to response and corresponding 95% confidence interval. Cox regression exploratory analysis will be used to estimate the hazard ratio with corresponding 95% confidence intervals for time to tumor volume reduction of at least \geq 20% as a function of baseline characteristics (duration of disease, dose at V2, dose reduction, visual field (abnormal/normal), and α subunit at V1).

Logistic regression will be performed to explore association between baseline characteristics and tumor response.

Frequency and percentage of patients who present improvement of symptoms related to tumor compression, pituitary hormonal dysfunction, alpha subunit level normalization, will be presented for each symptom at each time point with associated exact 95% CI.

Incidence rates of pituitary hormonal dysfunction, normalization of alpha subunit level and proportion of patients with 50% reduction in alpha subunit level along with its exact 95% CI will be reported at baseline, Week 4, 12 and 24. Analyses for alpha subunit level will be repeated with per protocol population set and for the subgroup of patients with elevated alpha subunit level at baseline.

Hormone profiles, alpha subunit levels and will be summarized at each time point in terms of frequency (N), mean, standard-deviation, median, minimum, and maximum.

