  - End of Study and safety visits timepoints added to  $28 \pm 3$  days and  $56 \pm 3$  days after the administration of the last dose of the study medication, respectively, for extension phase patients who discontinue treatment
- 7 Visits and evaluations schedule
  - On Table 7-1
    - The information that  $a \pm 3$  day window will be allowed for scheduled visits has been deleted.
    - Clarification on item 10 that if the visual field evaluation at Screening is performed no more than 14 days after Visit 2, it may be considered baseline data and there is no need to repeat it for Visit 2
    - Item 15 deleted: At the Screening Visit and Visit 10 (EOS), blood glucose and insulin will be measured at fasting at timepoint 0 during OGTT, and will be considered as baseline data for OGTT. Regarding this change, the glucose and insulin OGTT evaluation has also been deleted from the table
  - Added Table 7-2 Visits and evaluations schedule for the Extension Study with its specifications
- 7.3 Treatments
  - Replacement of the word responsibility with accountability
  - It has been clarified that Extension Phase patients will receive the medication starting on Week 24 and every 4 weeks  $(28 \pm 3 \text{ days})$  thereafter, until Week 92
- 7.4.1 Primary efficacy evaluation
  - Evaluation timepoints added on Weeks 48, 72, and 96 in the Extension Phase
- 7.4.2 Secondary efficacy evaluations
  - Visits 13, 16, 19, 22, 25, and 28 of the Extension Phase added for recording of disease-related symptoms
  - Clarification that symptoms not described in the section will be evaluated as absent or present
  - Weeks 48, 72, and 96 added for efficacy evaluation
- 7.5.2.1 Changes in blood glucose
  - 2008 ADA Position statement replaced by the 2010 statement
  - For consistency purposes, in the pasireotide clinical trials program (SOM230), blood glucose minimum levels have been changed from 200 to 275 mg/dL, as well as HbA1c percentage from 8 to 10%

- 7.5.2.2 Changes in QT interval
  - It has been clarified that if the ECG is abnormal at Visit 10 and no additional pasireotide LAR dose is administered, then the follow-up is at the investigator's discretion
  - It has been clarified that, on Scenario B of ECG change, the Holter ECG test must be recorded as soon as possible, within 7 days after the initial abnormal ECG, and not 30 minutes before dosing on the next pasireotide LAR administration day
  - Figure 7-1
    - Week 6 has been replaced with week 7 for QTcF evaluation

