#### 3.2.1 Secondary objective endpoints

The secondary variables are:

- Mean change in tumor volume evaluated by pituitary MRI between baseline and weeks 4, 12, 24, 48, 72, and 96.
- Percent change in tumor volume evaluated by pituitary MRI between baseline and weeks 4, 12, 24, 48, 72, and 96.
- Proportion of patients reaching tumor volume decrease of at least  $\geq$  20% after 4, 12, 48, 72, and 96 weeks of treatment.

- Time to treatment response for treatment responders, defined as the time from the date of the first injection to the first evaluation in which the patient reached a tumor volume decrease of at least ≥ 20%.
- Change in grading score of disease-related symptoms between baseline and weeks 4, 12, 24, 48, 72, and 96.
- Incidence of pituitary hormone dysfunction at baseline and on weeks 4, 12, 24, 48, 72, and 96.
- Proportion of patients reaching alpha subunit decrease of at least 50% on weeks 4, 12, 24, 48, 72, and 96.
- Proportion of patients reaching alpha subunit normalization on weeks 4, 12, 24, 48, 72, and 96.
- Percentage of adverse events with CTC grade  $\geq 3$  during treatment with pasireotide LAR.
- Percentage of patients with at least one adverse event with CTC grade  $\geq 3$ .
- Incidence of all adverse events, incidence of abnormal lab values, and summary of laboratory evaluations.
- For the extension phase: among patients who had been considered as responders (i.e., patients reaching a tumor volume decrease of at least 20% compared to initial tumor volume), to evaluate the number and proportion of patients who remained responsive during the extension phase treatment (according to the magnetic resonance imaging evaluations on weeks 48, 72, and 96).
- To evaluate the percentage of patients remaining with stable tumor volume during the study, i.e., patients who mantained tumor volume variation lower than 20% compared to baseline tumor volume (according to magnetic resonance imaging evaluations on weeks 24, 48, 72, and 96).
- If applicable, to evaluate whether there was a difference in response among patients on 40 and 60 mg doses of pasireotide LAR.

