# 7.4.2 Secondary efficacy evaluations

Tumor volume will also be evaluated as described on Section 7.4.1. Time to response will also be obtained (i.e., time to reach tumor volume decrease  $\geq 20\%$ ).

Disease-related symptoms will be reported by patients and recorded by the medical staff, on all Main Phase visits and on visits 13 (week 36), 16 (week 48), 19 (week 60), 22 (week 72), 25 (week 84), and 28 (week 96) of the Extension Phase.

Disease-related symptoms to be evaluated: headache, visual disorders, fatigue, decreased libido. Only for men: erectile dysfunction. Only for non-menopausal women: irregular or interrupted menstrual cycles. The investigator will also ask patients to classify the symptoms above according to a 5-point scale (0 = absent, 1 = mild, 2 = moderate, 3 = severe, 4 = very severe). The remaider will be evaluated as absent or present.

Hormone profiles, including growth hormone (GH), insulin-like growth factor I (IGF-1), follicle-stimulating hormone (FSH), luteinizing hormone (LH), adrenocorticotropic hormone (ACTH), thyroid-stimulating hormone (TSH), prolactin (PRL), cortisol, free T4, and estradiol (for women) or testosterone (for men), will be evaluated in the Screening Period (and will be considered as baseline data) and on Weeks 4, 12, and 24 of the Main Phase. Evaluations in the Extension Phase will be performed on Weeks 48, 72, and 96.

Alpha subunit levels will be measured in the Screening Period (and will be considered as baseline data), on Weeks 4, 12, and 24 in the Main Phase, and on Weeks 48, 72, and 96 in the Extension Phase.

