# 10.5.1 Efficacy variables and analysis

The secondary efficacy endpoints are described on section 3.3.2.

The changes in mean and percent tumor volume variation from baseline to Weeks 4, 12, and 24 will be presented together with the 90% confidence interval (90% CI). If the data are in a non-normal distribution, median CI will also be generated. The incidence rate of patients with tumor volume decrease  $\geq$  20% and its exact CI will be reported on weeks 4 and 12.

Summary of the statistical analyses will be provided for each disease-related symptom (headache, visual disorders, fatigue, decreased libido, and specific symptoms for men and women) on each visit. Changes in baseline scores will be summarized on each visit for all symptoms.

The time to response, defined as the time from the first injection to the first evaluation in which a patient reaches a tumor volume decrease of at least  $\geq 20\%$ , will be listed for all patients. If a patient did not reach tumor response, the period of his/her last evaluation will be used as a cutoff period. For responsive patients, average time to response will be summarized.

Additionally, logistic and cox regression models may be used to explore the association between baseline characteristics and tumor response and time to tumor response. These analyses will be specified in the report analysis plan (RAP).

The frequency and percentage of patients experiencing improvement of symptoms related to tumor compression, pituitary hormone dysfunction, normalization of the alpha subunit level, will be presented for each symptom at each period with the associated exact 90% CI.

The incidence rates of pituitary hormone dysfunction, the normalization of alpha subunit levels, and the proportion of patients with a 50% decrease in the alpha subunit level, together with the exact 90% CI will be reported at baseline and on weeks 4, 12, and 24. The alpha subunit level analyses will be performed again with the population set according to protocol and for the subgroup of patients with increased alpha subunit levels at baseline.

Hormone profiles, alpha subunit levels, in each period in terms of frequency (N), mean, standard deviation, median, minimum, and maximum.

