5.6 SAMPLE SIZE RATIONAL

This is a proof of concept study. The sample size of 19 evaluable patients was selected without regard for statistical power. A response rate (proportion of patients with tumor volume reduction ≥ 20%) of at least 10% is considered clinically meaningful for this patient population. **Table A 3**, presents for various assumed response rates the probability of having two or more responders. If the true response rate is 10%, the probability of getting two or more responders out of 19 patients is 58%. In this trial the 90% CI will also be obtained. **Table A 4**, presents the exact 90% CI when 2-6 patients respond out of the 19 patients. Considering the dropout of 20%, we will enrol 23 patients to get 19 evaluable patients for final analysis.

Table A 3: Probability of getting ≥ 2 response in a sample of 19 patients

Assumed p	0.05	0.10	0.15	0.20	0.25	0.30
P(X ≥ 2)	25%	58%	80%	92%	97%	99%
X is assumed to have	binomial distri	bution with	probability	р		

Table A 4: Resulting 90% CIs for various number of observed responders

Responders/n	Lower confidence limit	Upper confidence limitl
2/19	1.9%	29.6%
3/19	4.4%	35.9%
4/19	7.5%	41.9%
5/19	11%	47.6%
6/19	14.7%	53%

6 Study Results

The study results are presented in Appendix 1: Statistical Tables – Core study phase.

The extension study results are presented in Appendix 2: Statistical Tables – Extension study.

7 Clarifications to the study protocol

The following clarifications to the study protocol were considered on this SAP:

- Clarification of statistical analysis for time to response and baseline characteristics
- Definition of treatment-emergent adverse events
- Definition of comparative analysis of hormonal parameters
- Confidence interval of 95% instead of 90% due to the standard approach in clinical epidemiology

Any deviations from methodology/definitions/analysis described on this SAP should be previously accepted by the sponsor and documented (together with reasoning, if relevant) in the statistical analysis report.

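### The SAP's symptom analysis leaves out decreased libido, and its symptom tables have no score-change row for the retained symptom-score endpoint

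*SAP*

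**What the plan says.** **Protocol.** Section 3.2.1 sets one symptom-score endpoint: "Change in grading score of disease-related symptoms between baseline and weeks 4, 12, 24, 48, 72, and 96". Section 10.5.1 plans summaries for "headache, visual disorders, fatigue, decreased libido, and specific symptoms for men and women) on each visit", and also for score changes in all symptoms.

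Section 7.4.2 names headache, visual disorders, fatigue and decreased libido, then erectile dysfunction for men and menstrual irregularity for non-menopausal women. It continues: "The investigator will also ask patients to classify the symptoms above according to a 5-point scale", running from 0 (absent) to 4 (very severe). The scale is followed by one further sentence: "The remaider will be evaluated as absent or present". Which symptoms form that remainder is not stated.

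**SAP.** Section 1.2 lists all six symptoms, and 1.2.1 keeps the score-change endpoint. A footnote to Table A 1 repeats the six symptoms, the 0–4 scale and an absent/present category for the others. Section 5.5.1 names "headaches, visual disturbance, fatigue, symptoms specific to man and woman) at each visits" and then promises score changes for every symptom at each visit.

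**Shells.** Tables 10 and B 5 contain the same five blocks: headache, visual disturbances and fatigue in five grades, and erectile dysfunction and regular menses as yes/no. Each block has an improved yes/no line.

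**Recorded changes.** SAP section 7 opens with "The following clarifications to the study protocol were considered on this SAP" and gives four items: the time-to-response and baseline-characteristics analysis, the definition of treatment-emergent events, the comparison of hormonal parameters, and 95% in place of 90% confidence intervals. None concerns symptoms.

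**The concern.** A symptom that the protocol names for analysis disappears between protocol and SAP with no reason given. Symptom assessments are scheduled throughout the main phase and marked for entry in the database, so a programmer working from the shells would leave a planned and scheduled symptom unreported. In an open-label, single-arm study, an unexplained gap in a prespecified list invites a question about selective reporting.

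There is also a mismatch between endpoint and tables. The endpoint is a change in score, whereas the shells show how many patients fall in each category at each visit and whether each patient improved. For erectile dysfunction and menses, a yes/no table could not show a shift from severe to mild, if a grade was in fact recorded.

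**Working it through.** No design figure (alpha, power, effect size, dropout) bears on this point, and the plan states no figure to reproduce. The check compares the two documents symptom by symptom.

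| Symptom | Protocol 10.5.1 | Protocol 7.4.2, literal reading | SAP 1.2 | SAP 5.5.1 list | Tables 10 and B 5 |
|---|---|---|---|---|---|
| Headache | yes | 0–4 | yes | yes | five grades |
| Visual disorders | yes | 0–4 | yes | yes | five grades |
| Fatigue | yes | 0–4 | yes | yes | five grades |
| Decreased libido | yes | 0–4 | yes | **no** | **no block** |
| Erectile dysfunction | yes (sex-specific) | 0–4 | yes | yes (sex-specific) | yes/no |
| Menses | yes (sex-specific) | 0–4 | yes | yes (sex-specific) | yes/no |

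Shell count: 3 graded + 2 yes/no + 1 absent = 6. Rows for change from baseline in score: 0 of 6.

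**Libido.** The phrase about symptoms specific to men and women does not cover it, because Protocol 10.5.1 and 7.4.2 both list libido separately from the sex-specific items. Lost table rows are an unlikely explanation: the SAP text and two separate shells agree. The omission stands whichever scale libido was recorded on.

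**Grading of erectile dysfunction and menses.** Three things favour 0–4:
- Section 7.4.2 tells patients to "classify the symptoms above according to a 5-point scale" after all six symptoms have been named.
- The synopsis gives the same list and scale without the remainder sentence.
- The summary of changes explains that sentence as a "Clarification that symptoms not described in the section will be evaluated as absent or present", which would exclude the six. I use it only as an aid to reading the current text.

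Against this, the current text leaves the remainder undefined, and the eCRF fields are not shown.

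**Score change.** Grade counts by visit do not show each patient's change. The improved line counts falls of at least one point but places unchanged and worsened patients together under No. Neither item is a summary of change in score, for any symptom.

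**Footnote b.** In both shells this footnote counts a move from No at Visit 1 to Yes later as improvement. That direction is right for regular menses (footnote c). For a row labelled erectile dysfunction it is reversed: new dysfunction would be counted as benefit, and resolution, Yes to No, would not be counted as improvement.

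**The case against.** The strongest reply has three parts.

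1. The SAP has not abandoned the endpoint. Sections 1.2 and 1.2.1 keep it, 5.5.1 promises score changes for all symptoms, and three symptoms remain fully graded. This stands. A reader might infer from the shells that the symptom-score endpoint is not analysed at all. The documents do not support that: what they show is a SAP that contradicts itself and shells that are incomplete.

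2. The protocol itself allows binary recording for some symptoms. Section 7.4.2, a footnote to Table 7-1 and the SAP's Table A 1 footnote all carry an absent/present category. Section 7.4.2 introduces the two sex-specific symptoms apart from the others, so reading the remainder as those two is possible and would match the shells. This stands in part. The wording favours 0–4 but does not settle it, so it cannot be stated as fact that the SAP changed the scale, or that a severe-to-mild change is lost. Both depend on what the eCRF holds.

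3. This is a descriptive secondary endpoint in a small proof-of-concept study. That is true and limits the weight of the point. It does not explain why libido was dropped.

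A reader might also infer that three of the six symptoms are analysed exactly as the protocol specifies. That is too generous to the shells: even those three lack a score-change summary.

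**Conclusion.** The omission of decreased libido is confirmed and needs no interpretation: Protocol 10.5.1 and SAP 1.2 include it, SAP 5.5.1 and both shells do not, and section 7 is silent. One of six symptoms would go unreported if the shells were followed. It is also confirmed that no symptom has a score-change row, so the shells as drafted do not deliver the endpoint kept in SAP 1.2.1.

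The yes/no layout of erectile dysfunction and menses is confirmed as a description of the shells. As a departure from the protocol it is probable but conditional, resting on the reading of section 7.4.2 and on eCRF content that the documents do not show. The reversed footnote b is an error as the row is labelled.

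Nothing here touches the primary endpoint. The effect is confined to descriptive symptom reporting in a study enrolling 23 patients to obtain 19 evaluable, with the sex-specific items applying only to part of that group. The SAP should be corrected because the gap is plain and the repair is small.

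**What to change.** - Restore decreased libido in the SAP 5.5.1 list and add a libido block to Tables 10 and B 5.
- Add change-from-baseline score rows to both tables for every symptom graded 0–4. Extending the one-point improvement flag alone would not deliver the endpoint.
- State in SAP 5.5.1 which symptoms are graded and which are binary, matching the eCRF. Where the 0–4 score was collected for erectile dysfunction and menses, use it. If only yes/no was collected, list that format, with its reason, in SAP section 7.
- If yes/no is kept for erectile dysfunction, correct footnote b in both tables so that improvement is a move from Yes to No. Footnote c for regular menses can stay.

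The cost is a sentence or two in the SAP, some shell rows, one footnote and a check of the eCRF. No new visit or assessment is needed, since symptoms are already scheduled in both phases and marked for database entry.

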1.2.1 End-points for secondary objectives

The secondary variables are:

Mean change of tumor volume assessed by pituitary MRI from baseline to Week 4, 12, 24, 48, 72 and
 96.

- Percent change of tumor volume assessed by pituitary MRI from baseline to Week 4, 12, 24, 48, 72 and
 96.
- Proportion of patients achieving tumor volume reduction of at least ≥ 20% after 4, 12, 48, 72 and 96 weeks of treatment.
- Time to treatment response for treatment responders, defined as the time from the date of first injection to the first evaluation the patient achieves tumor volume reduction of at least >20%.
- Change from baseline to Week 4, 12, 24, 48, 72 and 96 in disease-related symptoms scores.
- Incidence of pituitary hormonal dysfunction at baseline and at Weeks 4, 12, 24, 48, 72 and 96.
- Proportion of patients achieving alpha subunit reduction of at least 50% at Weeks 4, 12, 24, 48, 72 and 96.
- Proportion of patients achieving normalization of alpha subunit at Weeks 4, 12, 24, 48, 72 and 96.
- Percentage of CTC (≥3) adverse events during treatment with pasireotide LAR.
- Percentage of patients with at least one adverse event with CTC grade ≥ 3.
- Incidence of all adverse events, incidence of laboratory abnormal values and summary of laboratory assessments.
- For extension phase: among patients who had been considered as responsive (*i.e.*, patients who achieved a reduction in tumor volume of at least 20% with respect to the initial tumor volume), assess the number and proportion of patients that remained responsive during the treatment period of extension phase (according to estimates by magnetic resonance at weeks 48, 72 and 96).
- To assess the percentage of patients who remained with tumor volume stable during the study, *i.e.* patients who maintained tumor volume with variation less than 20% with respect to the basal tumor volume (according to evaluations by magnetic resonance imaging at weeks 24, 48, 72 and 96).
- If applicable, assessing whether there was difference in response between patients using dose of 40 and 60 mg of pasireotide LAR.

2 Study design

This is a prospective, multicenter, open-label, single arm, phase II study to evaluate the efficacy and safety of pasireotide LAR in adult patients with NFPA.

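### The SAP's time-to-response analysis targets an all-patient Kaplan-Meier median with at most about a 3% chance of existing in its own planning range, and one Cox covariate is constant by design

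*SAP*

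**What the plan says.** SAP 1.2.1 lists the endpoint as "Time to treatment response for treatment responders, defined as the time from the date of first injection" up to the first evaluation showing a volume reduction of at least 20%. Protocol 3.2.1 has the same definition. For the analysis, Protocol 10.5.1 lists the times for all patients, gives non-responders a cut-off at their last evaluation, and adds: "For responsive patients, average time to response will be summarized". It allows Cox and logistic models as an option.

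SAP 5.5.1 keeps the listing and the censoring at last assessment, drops the responder average, and adds: "Kaplan-Meier analysis will be performed for time to response aiming to compute the median time to response and corresponding 95% confidence interval". Table 8 asks for N, events, censored, mean, median, 25th and 75th percentiles and range, and Figure 3 is the Kaplan-Meier curve. Neither the text nor Table 8 keeps an explicit responder-only summary. SAP 7 declares a clarification of the time-to-response analysis but gives no reason for it.

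SAP 5.5.1 also plans an exploratory Cox model on duration of disease, dose at V2, dose reduction, visual field and alpha subunit. Table 9 has 60 mg and 40 mg columns for dose at V2. A further sentence, "Logistic regression will be performed to explore association between baseline characteristics and tumor response", names no covariates and no fitting method.

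On size, SAP 5.6 says "The sample size of 19 evaluable patients was selected without regard for statistical power" and "Considering the dropout of 20%, we will enrol 23 patients to get 19 evaluable patients for final analysis". Its Table A 3 covers response rates of 5% to 30%, and Table A 4 "presents the exact 90% CI when 2-6 patients respond out of the 19 patients".

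**The concern.** The endpoint asks how long responders took to respond. The all-patient median answers a different question, namely when half of all patients will have responded. Where a minority is expected to respond, that question usually has no answer. Followed as written, the SAP would report *not reached* for the statistic it sets out to compute, and would contain no stated summary of the quantity the endpoint defines. It gives no fallback.

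The exploratory models raise a related, smaller problem. With 2 to 6 events, ordinary Cox or logistic fits can meet an empty cell, which gives an infinite ratio and an uninformative Wald interval. The SAP sets no minimum event count and no method for this case. Separately, a covariate that takes one value in every patient has no hazard ratio.

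**Working it through.** **Inputs.** n = 19 evaluable, 23 enrolled, response rates 5% to 30%, and 2 to 6 responders (SAP 5.6). Follow-up MRIs in the Main Phase are at Weeks 4, 12 and 24 (Protocol 4). The split of the binary covariates is not in the documents; 50:50 and 30:70 are assumed, independent of response.

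**1. The plan's own figures.** P(X ≥ 2) for X ~ Bin(19, p) gives 24.5, 58.0, 80.2, 91.7, 96.9 and 99.0% at p = 0.05, 0.10, 0.15, 0.20, 0.25 and 0.30, matching Table A 3. Exact 90% limits run from 1.9–29.6% (2/19) to 14.7–53.0% (6/19), matching Table A 4.

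**2. Percentiles of time to response.** With complete follow-up the cumulative curve ends at X/19. The 25th percentile needs X ≥ 5 (5/19 = 26.3%; 4/19 = 21.1%). The median needs X ≥ 10 (10/19 = 52.6%; 9/19 = 47.4%). The 75th needs X ≥ 15 (15/19 = 78.9%; 14/19 = 73.7%).

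| Response rate | P(X ≥ 5) | P(X ≥ 10) | P(X ≥ 15) |
|---|---|---|---|
| 10% | 3.5% | 0.0004% | below 0.002% |
| 20% | 33% | 0.16% | below 0.002% |
| 30% | 72% | 3.3% | below 0.002% |

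At the top of the planned responder range, 6/19 = 31.6%, so with complete follow-up no count in Table A 4 yields a median. Early censoring can lift the curve, but barely: simulating 23 patients with 20% dropout censored gives 0.15%, 0.9% and 3.3% at rates of 20%, 25% and 30%. The chance of X ≥ 10 is 19% at a 40% rate and 50% at a 50% rate.

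**3. Empty cells for a binary factor.** Given k responders and factor prevalence q, all responders fall on one side with probability q^k + (1 − q)^k. The chance that all non-responders do so is small and is included below.

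| Responders k | 2 | 3 | 4 | 5 | 6 |
|---|---|---|---|---|---|
| q = 0.5 | 50% | 25% | 13% | 6% | 3% |
| q = 0.3 | 58% | 37% | 25% | 18% | 13% |

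Weight these by the binomial probabilities of k = 2 to 6. At a 10% rate the weights are 0.2852, 0.1796, 0.0798, 0.0266 and 0.0069, which sum to 0.578. For q = 0.5 the weighted sum is 0.1426 + 0.0449 + 0.0100 + 0.0017 + 0.0002 = 0.1994, and 0.1994/0.578 = 34.5%. At rates of 15%, 20% and 30% the same step gives 26.8%, 20.3% and 11.7%. For q = 0.3 the four figures are 45%, 38%, 31% and 23%.

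**4. Continuous covariates fitted singly.** Responders hold all the highest or all the lowest values with probability 2/C(19, k): 2/171 = 1.2% at k = 2, 2/969 = 0.2% at k = 3, and below 0.1% from k = 4. Duration of disease and alpha subunit therefore rarely separate.

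**5. Dose at V2.** Protocol 6.4 (Main Phase Treatment) gives the first dose, at Visit 2, as 60 mg, and allows a lower dose only for safety reasons afterwards. The 40 mg column for V2 in SAP Table 9 has no patients under the protocol, so the hazard ratio is undefined at any response rate.

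**The case against.** The best defence is proportion. This is a proof-of-concept study sized without regard to power, the regressions are exploratory, and the primary endpoint is untouched. A median that is not reached is a legitimate result, and the SAP only aims to compute it. The change is declared in SAP 7. Response rates with exact intervals are already planned at Weeks 4, 12 and 24. The 5% to 30% range illustrates the Week 24 rate, and first response at any MRI may be more frequent. All of this is fair and limits the weight of the point. It does not rescue the target: the median becomes likely only near a 50% rate, and response rates at each visit are not cumulative first response.

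Three stronger readings are tempting, and the documents do not support them.

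- *The analyses would return almost nothing.* The curve, the event and censoring counts and the listing all survive, and the 25th percentile is estimable in 72% of trials at a 30% rate.
- *Infinite hazard and odds ratios would dominate the planned range.* Without conditioning on 2 to 6 responders, the empty-cell chance at a 10% rate is 62% for a 50:50 factor. But 42 points of that come from trials with 0 or 1 responder, where an empty cell is automatic (0.420 + 0.199 = 0.619). The factor split is assumed, continuous covariates seldom separate, and Table 9 shows one hazard ratio per covariate, which suggests separate fits.
- *Censoring of withdrawals inflates the curve materially.* No size can be put on this, and Protocol 6.4.4 schedules all Visit 10 evaluations 28 ± 3 days after the last dose for Main Phase early leavers, so response is checked at exit.

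**Conclusion.** The point holds for the target of the time-to-response analysis. The SAP substitutes a statistic with at most about a 3% chance of existing across its own planning range, and drops the responder summary that matches the endpoint definition. This rests on a binomial count of first responders among 19 patients; censoring at the planned dropout leaves it essentially unchanged.

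The point also holds, with certainty under the protocol, for dose at V2. For the remaining exploratory fits it holds in moderate form: given 2 to 6 responders, a binary factor has an empty cell in about 34.5% down to 12% of trials (assumed 50:50 split) or 45% down to 23% (assumed 30:70 split), as the response rate goes from 10% to 30%. These models are at risk rather than bound to fail. A secondary endpoint and exploratory work are affected; the primary analysis is not.

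**What to change.** In SAP 5.5.1 and Table 8:

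- Restore a responder-only summary of time to response: n, median or mean, and range.
- Make cumulative first response at Weeks 4, 12 and 24, with confidence intervals, the target in place of the median. Responses are scheduled to be seen only at these three MRIs, so little is lost. Show the Kaplan-Meier median and quartiles as *not reached* where that applies.

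In the Cox model and Table 9:

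- Remove dose at V2. The 40 mg column there and the Visit 2 dose in Protocol 6.4 must be reconciled.

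For the exploratory Cox and logistic models:

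- Fit one factor at a time and state either a penalised or exact method, or a minimum number of responders below which only descriptive tables are given. The choice between these is partly preference.

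Treating withdrawals as competing events is optional. The cost is edits to SAP text and table shells, with no new data and no patients.
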